#### **6.6.7. Immunogenicity**

Immunogenicity analysis will be based on the immunogenicity analysis population which will be the same as the safety analysis population and will include anti-drug antibody and neutralizing antibody development by Week 97 and until the end of follow-up. Both continuous endpoints (titer) and categorical endpoints (ie, positive, negative and inconclusive) will be reported for the anti-drug antibody and neutralizing antibody assays by dose and sampling time points. Data permitting, the incidence of anti-drug antibody and

neutralizing antibody will be summarized by time points within each dose cohort, sequence, and may be also summarized by dose. The impact of anti-drug antibody and neutralizing antibody on PK and PD parameters and profiles, efficacy and safety may be also evaluated but no statistical inference will be drawn.

The immunogenicity of Process 1 material may be assessed from Sequence 1 and 2 for Period 1, and Sequence 2 of Period 2. To assess the immunogenicity of PF-06252616 Process 2 material, it is necessary that the subjects did not receive any prior administration of PF-06252616 Process 1 material. This may be obtained from subjects in Sequence 3 who received Placebo in Period 1 and receive drug product for the first time as Process 2 material in Period 2.

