## Study Design

This is a Phase 2 randomized, 2-period, double-blind, placebo-controlled, multiple ascending dose study to evaluate the safety, efficacy, PK and PD of PF-06252616 administered to ambulatory boys diagnosed with DMD. Three IV infused dose levels (5, 20 and 40 mg/kg) administered every 28 days will be investigated in a within subject dose escalating fashion.

Approximately 105 eligible subjects will be randomly assigned to 1 of 3 sequence groups and receive investigational product for approximately 96 weeks (2 treatment periods of approximately 48 weeks each) stratified by their baseline time to complete the 4 stair climb (either  $\leq$  or  $>8$  seconds).

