### Sequence 3 (n=35):

Period 1: Placebo

Period 2: Active treatment (PF-06252616) within subject dose escalation (5, 20 and 40 mg/kg)

Each dose level will be explored in a dose escalating fashion within subjects, starting with the lowest dose. At each dose level, dosing will be administered over a 2-hour IV infusion every 4 weeks for a total of 16 weeks (4 doses). Dose escalation within a subject will occur following the planned fourth dose within each dose level. Subjects will move from Period 1 to Period 2 without a pause between periods.

Individual dose escalation decisions will be conducted for each subject by the Investigator, sponsor Medical Monitor and a Designated Reviewer. This process will occur from time of the first subject being enrolled and continue until the time of the IA. At the time of IA (or sooner as determined by the External Data monitoring committee's review of unblinded data), if adequate safety has been demonstrated at each dose level as determined by an External Data Monitoring Committee (E-DMC), subsequent dose escalation will occur without confirmation of the individual safety data prior to dose escalation.

From the time of study initiation through completion of the study, the sponsor will conduct routine safety monitoring of the blinded data per the safety review plans. In addition, the E-DMC will review unblinded safety data. The E-DMC may determine if it is necessary to close or adjust a dose level within the study or continue with individual level dose escalation review.

In the event that the E-DMC determines that adequate safety has been established at each dose level (following the IA or sooner), they will also consider if the requirement for liver MRI can be reduced to an annual safety assessment (based on normal findings on the liver MRI).

The individual subject dose adjustment will be determined by three parties including the Investigator, sponsor Medical Monitor and a Designated Reviewer. Following the planned fourth dose within each dose level, all available safety data for an individual subject will be reviewed by the Investigator, sponsor Medical Monitor and Designated Reviewer to determine the appropriate dose adjustment.

Dose adjustment criteria will be used to determine if the dosing or dose level should be:

- Escalated to the next dose level.
- Maintained at the current dose level.
- Reduced to a lower dose level, or
- Stop dosing.

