#### 1.8.2. Immunogenicity Results B5161001

The immunogenicity assessment population included all 53 subjects who received the active study drug (PF-06252616) with at least 1 post-treatment anti-drug antibody (ADA) determination. The impact of ADAs and neutralizing antibodies (NAbs) on PK and PD were also evaluated graphically with no apparent differences in PK and PD profiles between ADA positive subjects and ADA negative subjects.

090177e1909dc770\Approved\Approved On: 25-Mar-2019 05:50 (GMT)

In subjects receiving active PF-06252616, ADAs were detected early on Day 15 of the study. Overall incidence of ADA was noted in 6 out of 53 subjects who received active treatment (PF-06252616) in the following cohorts; 1 subject in 1 mg/kg, 10 mg/kg (single IV), 10 mg/kg (repeat dose) and 20 mg/kg IV dose cohorts; 2 subjects in 3 mg/kg SC dose cohort. The confirmed incidence rate was 11.3%. There were 14 subjects who were considered inconclusive and the inconclusive subject-adjusted incidence rate excluding these subjects was 15.4% (6 out of 39 subjects). Samples which tested positive for ADA were further tested for NAb. A total of 5 samples from 4 subjects showed NAb titer  $\geq 1.3$  in the following cohorts: 1 each in the 1 mg/kg, 10 mg/kg (repeat), 20 mg/kg IV, and 3 mg/kg SC group. Although these samples were positive in the NAb assay, all were determined to have 'inconclusive' results for neutralizing activity due to potential interference from PF-06252616 levels in these samples.

In summary, for Study B5161001, there was a confirmed ADA incidence rate of 11.3% but without any obvious impact on the PF-06252616 PK or myostatin modulation.

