#### 2.2.3.4. Immunogenicity

Incidence of ADA and NAb development by Week 97.

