## 5. STUDY TREATMENTS

For the purposes of this study, and per International Conference on Harmonization (ICH) guidelines, investigational product is defined as a pharmaceutical form of an active ingredient or placebo being tested or used as a reference in a clinical trial, including a product with a marketing authorization when used or assembled (formulated or packaged) in a way different from the approved form, or when used for an unapproved indication, or when used to gain further information about an approved use (ICH E6 1.33).

PF-06252616 is incompatible with sodium chloride containing solutions. Therefore, do not use Normal Saline (0.9% sodium chloride) or other sodium chloride containing solutions, as a diluent or for flushing the infusion line. Dextrose 5% solution is recommended for use during flushing to ensure complete delivery of the prepared dosing solution. Refer to the Investigational Product Manual and the Administration Card for details regarding the preparation and administration of this investigational product.

Subjects will be treated with IV infused PF-06252616 or placebo in this double-blind, placebo controlled study. Please refer to the dosage and administration instruction in the Investigational Product Manual for complete information on storage, stability, preparation and administration of both investigational drug products (PF-06252616 and placebo).

This study is a 3-sequence group, double-blind, placebo controlled, randomized clinical trial. Subjects will be randomized to one of 3 sequence groups and will receive treatment on a 28 day schedule, per the [Schedule of Activities](#). Each subject will have the opportunity to receive a total of four doses of each dose level every four weeks. The dose will be calculated based on the subject weight, which will be obtained at each visit prior to each infusion. Either the current weight or the prior month's weight may be used to provide this calculation with the exception of Day 1. At Day 1 the weight from the Baseline visit should be used to calculate Day 1 dose. The following tables depict the dosing schedule in Period 1 and 2 for each Sequence group.

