## **4.3. Safety Analysis Set**

The Safety Analysis Set is defined as all subjects who receive at least 1 dose of investigational drug.

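### The immunogenicity population in SAP 6.6.7 includes boys never given PF-06252616 and boys with no post-dose ADA result, so an overall or Sequence 3 ADA/NAb incidence can be somewhat understated

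*SAP*

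**What the plan says.** The secondary endpoint in Protocol 2.2.3.4 is "Incidence of ADA and NAb development by Week 97". SAP 6.6 lists the same incidence among the safety summaries, and SAP 6.6.7 analyses it in an "immunogenicity analysis population which will be the same as the safety analysis population". SAP 4.3 reads: "The Safety Analysis Set is defined as all subjects who receive at least 1 dose of investigational drug". It requires neither a dose of PF-06252616 nor an ADA result.

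Placebo counts as investigational drug. Protocol section 5 states that "investigational product is defined as a pharmaceutical form of an active ingredient or placebo being tested", and the same section refers to PF-06252616 and placebo together as the investigational drug products. SAP 6.6.1 compares adverse events with placebo, which needs placebo boys in the safety set.

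Other populations are stricter. The PK sets (SAP 4.4.1 and 4.4.2) require a PF-06252616 dose and a reported result. The GDF-8 sets (SAP 4.4.3 and 4.4.4) require a result. Protocol 1.8.2 describes the Phase 1 immunogenicity population as those "who received the active study drug (PF-06252616) with at least 1 post-treatment anti-drug antibody (ADA) determination".

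SAP 6.6.7 reports positive, negative and inconclusive as separate categories. Data permitting, it summarizes incidence by time point within dose cohort and sequence. It does not say how inconclusive boys enter an incidence denominator, and it plans no rate that excludes them.

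**The concern.** A boy who has never received PF-06252616 cannot develop antibodies in response to it. A boy with no post-dose sample cannot be shown to have developed them. Both add to the denominator and, apart from assay background, add nothing to the numerator. An incidence over the stated population is therefore pulled down, most of all in Sequence 3, where active drug starts only at Week 49 and every loss in Period 1 is a boy never exposed.

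The result would also rest on a different kind of population from the Phase 1 rate with which it is likely to be compared. Phase 1 gave two rates, one with and one without inconclusive subjects. Without the second rate here, a reader cannot tell directly how far the headline depends on boys whose antibody status was not established.

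**Working it through.** **Inputs**
- Randomized: "Approximately 105 eligible subjects will be randomly assigned to 1 of 3 sequence groups", 35 per sequence (Protocol, Study Design).
- Attrition: 10% before completing 49 weeks (Protocol 9.1). This is an overall planning figure. Its use for Sequence 3 alone is an assumption, written *d*.
- Sequence 3 receives its first active dose at Week 49, so a boy who leaves earlier is never exposed (Protocol Tables 3 and 4).
- Phase 1: 53 subjects, 6 ADA positive, 14 inconclusive (Protocol 1.8.2).

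**Step 1: reproduce the Phase 1 rates**
- All evaluable subjects: 6/53 = 11.3%.
- Excluding inconclusive: 6/(53 − 14) = 6/39 = 15.4%.

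Both agree with the protocol. The documents give no ADA rate for B5161002.

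**Step 2: never-dosed boys**

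Never-dosed boys number 35*d*. If none of them is ADA positive, the relative understatement is:
- overall: 35*d*/105 = *d*/3
- in a Sequence 3 rate: 35*d*/35 = *d*

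| *d* (assumed) | Never dosed | Overall, relative | Sequence 3, relative |
|---|---|---|---|
| 5% | 1.75 | 1.7% | 5% |
| 10% | 3.5 | 3.3% | 10% |
| 15% | 5.25 | 5.0% | 15% |
| 30% | 10.5 | 10.0% | 30% |

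Taking 15.4% as the true rate and *d* = 10%, the loss is 15.4 × 0.033 = 0.5 percentage points overall and 15.4 × 0.10 = 1.5 points in Sequence 3.

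**Step 3: dosed boys with no post-dose ADA result**

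The documents give no number. Each such boy lowers an overall rate by 1/105, about 1% relative, and a single-sequence rate by 1/35, about 3% relative.

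**Step 4: inconclusive results**

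The two Phase 1 rates differ by 15.4 − 11.3 = 4.1 percentage points, and the first is 39/53 = 0.736 of the second. This shows how much the choice mattered in Phase 1. It does not carry over to this trial, whose inconclusive share is unknown.

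**Step 5: NAb**

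In Phase 1 the NAb-positive samples were all judged inconclusive for neutralizing activity because of possible drug interference. There is no usable NAb rate to work from.

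**The case against.** The case on the other side is substantial, and most of it stands.

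- **Summaries that are not diluted.** SAP 6.6.7 plans incidence within dose cohorts, and a boy who only had placebo belongs to no active dose cohort. Its Process 2 assessment is limited to Sequence 3 boys who receive drug for the first time in Period 2. A reader might infer that the Process 2 immunogenicity result is diluted by boys lost in Period 1; the section's own wording excludes them.
- **Inconclusive boys in the denominator.** Phase 1 did the same: 6/53 is what Protocol 1.8.2 calls the confirmed rate and repeats as its summary. Calling that rate too low assumes that inconclusive subjects would be positive as often as conclusive ones. The separate inconclusive category in SAP 6.6.7 also lets a reader rebuild an adjusted rate.
- **Size.** A reader might infer an overall understatement of 10% or more. Never-dosed boys alone give about 3%. With *d* = 10%, the overall figure reaches 10% only if about 6.9% of exposed boys are inconclusive and their retention is treated as an error. Carrying over the Phase 1 share (14/53 = 26.4%) would give 28.9%, but that share comes from healthy adults, 42 of 53 of whom had a single dose (Protocol 1.11). Sequence 2 is also sampled through a drug-free Period 2, when drug interference should fade.
- **Reporting standards.** SAP 6.6 refers to sponsor data standards that are not in these documents and might set a narrower denominator. The endpoint is descriptive.

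None of this changes the population that SAP 6.6.7 names. For an overall or by-sequence Week 97 incidence, that population includes unexposed and unassessed boys.

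**Conclusion.** The point holds in a limited form. The stated population is wrong for an overall or Sequence 3 incidence of antibodies to the drug by Week 97. At an assumed 10% loss from Sequence 3 before its first active dose, ADA incidence is understated by about 3% relative overall and about 10% in a Sequence 3 rate, or roughly 0.5 and 1.5 percentage points on a 15.4% rate. These figures assume that never-dosed boys test negative. Boys without a post-dose determination add to the effect by an amount the documents do not allow to be estimated. For NAb the direction is the same, but the size cannot be given.

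The documents do not support a general claim of 10% or more, an effect of never-dosed boys on the Process 2 or dose-cohort results, or the view that keeping inconclusive boys is a mistake. On inconclusive results, the remaining gap is that the SAP does not plan the adjusted rate that Phase 1 reported beside its headline rate.

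**What to change.** In SAP 6.6.7, replace the link to the safety set with an immunogenicity set of boys who have at least one dose of PF-06252616 and at least one post-dose ADA determination. In addition:
- count Sequence 3 from its first active dose (Week 49, Day 337);
- show placebo-period samples separately, as assay background;
- report incidence both over all evaluable boys and over boys with a conclusive (positive or negative) result, as in Phase 1.

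The cost is SAP wording and one extra table column, with no new data collection. The reported incidence may be slightly higher.

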## 7. INTERIM ANALYSES

### 7.1. Introduction

One formal interim analysis will be performed for inferential purposes. *An interim analysis will be conducted after approximately 50% of the subjects have completed assessments at Week 49.* The primary purpose of this analysis is to test for interim futility or efficacy on the functional endpoint of the 4 stair climb. The decision making at the interim analysis will follow a 3-tier approach. For the first tier, *the futility and efficacy boundaries will be calculated based on the gamma family alpha- and beta-spending and conservative stopping boundaries ( $\gamma \leq -1$ ) will be implemented for the futility and efficacy boundaries.* The cutoff used at the interim analysis will be calculated based on the percentage of subjects included at the interim analysis to ensure appropriate protection of the type I error. The second and the third tiers will focus on 4SC test completers and on MRI variables, respectively (see CCI [REDACTED] for details). *A statistical and programming team independent from the study team will conduct all unblinded analyses to be forwarded to the external data monitoring committee (E-DMC) and will maintain the study blind per Pfizer's SOPs.* The programmers will create the datasets and analysis tables required for the interim analysis. Additional information concerning the composition and function of the E-DMC are contained in the E-DMC charter.

CCI [REDACTED]

CCI [REDACTED]

090177e1909dd632\Approved\Approved On: 25-Mar-2019 05:54 (GMT)

CCI

[Redacted]

CCI

[Redacted]

[Redacted]

[Redacted]

CCI

[Redacted]

090177e1909dd632\Approved\Approved On: 25-Mar-2019 05:54 (GMT)

[REDACTED]

[REDACTED]

CCI [REDACTED]

- [REDACTED]
- [REDACTED]
- [REDACTED]

[REDACTED]

[REDACTED]

090177e1909dd632\Approved\Approved On: 25-Mar-2019 05:54 (GMT)

CCI

**APPENDICES**

**Appendix 1. DATA DERIVATION DETAILS**

**Appendix 1.1. Definition and Use of Visit Windows in Reporting**

All windowing assignments will be reviewed by the study including any windowed visit with multiple observations more than 4 study days apart will be reviewed. Also any visits with no data will also be reviewed. Study windows may be adjusted to reflect appropriate data collection particular for the PK visits at weeks 2, 14, 18, 30, 34, and 46. The windowing definitions are included in Table 4. All windowing assignments are based on the relative study day. Relative study day 1 is always the first day of dosing.

**Table 4. Windowing Definitions**

Period	Visit Number	Efficacy Week Window	Study Day	
Pre-dose	1	Screening	-42 to -5	
	2	Baseline	--4 to 0	
Period 1	3	Week 1	1 to 3	
	4	Week 2	4 to 9	
	5	Week 5	10 to 43	
	6	Week 9	44 to 71	
	7	Week 13	72 to 88	
	8	Week 14	89 to 95	
	9	Week 17	96 to 116	
	10	Week 18	117 to 123	
	11	Week 21	124 to 155	
	12	Week 25	156 to 183	
	13	Week 29	184 to 200	
	14	Week 30	201 to 207	
	15	Week 33	208 to 228	
	16	Week 34	229 to 235	
	17	Week 37	236 to 257	
	Period 2	18	Week 41	258 to 295
		19	Week 45	296 to 312
20		Week 46	313 to 319	
21		Week 49	320 to 351	
22		Week 53	352 to 379	
23		Week 57	380 to 407	
24		Week 61	408 to 435	
25		Week 65	436 to 463	
26		Week 69	464 to 491	
27		Week 73	492 to 519	
28		Week 77	520 to 547	
29		Week 81	548 to 575	
Follow-up	30	Week 85	576 to 603	
	31	Week 89	604 to 631	
	32	Week 93	632 to 659	
	33	Week 97	660 to 701	
	34	Week 105	702 +	

090177e1909dd632\Approved\Approved On: 25-Mar-2019 05:54 (GMT)
